
9.7.3, Assessing Cirrhosis
	
(Insertion)
	
New: 9.7.3. Assessing Cirrhosis
 
To determine which dosing regimen subjects should follow, the presence or absence of cirrhosis should be assessed by the Investigator at Screening Visit 1. Acceptable methods of confirming (via medical history) or assessing cirrhosis for purposes of the study is defined as a subject who has documented evidence or presence of one or more of the following cirrhosis indicators:
 
 • Biopsy results consistent with PBC Stage 4 (Ludwig 1978) • Transient Elastography Median Value ≥ 16.9 kPa (Corpechot 2012) • The presence of any of the following (unless exclusionary per Section 8.3) in the absence of acute liver failure: 
 – Varices – Ascites – Radiological evidence of cirrhosis (nodular liver or enlargement of portal vein and splenomegaly) • Combined low platelet count ($<140\ 000/mm^3$) with: 
 – persistent decrease in serum albumin, or – elevation in prothrombin time /INR (not due to antithrombotic agent use), or – elevated bilirubin ($2\times$ ULN) 
Subjects who exhibit no evidence of cirrhosis by the above methods of assessment will be dosed using the Standard Dosing Regimen, while those who do exhibit evidence of cirrhosis by one or more of the above methods will be dosed using the Modified Dosing Regimen according to their Child-Pugh Score calculated in the electronic case report form (eCRF) (see Appendix A).
 
Cirrhosis status should be reassessed as clinically indicated throughout the study. Any change in
	
Added section to assess cirrhosis as this assessment will determine the acceptable dosing regimen based on a subject's Child-Pugh score.

-----------------------------------	--------------------	--	---

Section	Original Text (Amendment 1.1, 12 November 2015)	Revised Text (Version 3, 07 September 2016)	Justification for Change
		cirrhosis status will necessitate re-evaluation of the dosing regimen.	

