Section	Original Text (Amendment 3, 07 September 2016)	Revised Text (Version 4, 10 May 2017)	Justification for Change

Section 13.1.5 Additional Secondary Efficacy Analyses
	
Insertion
	
Progression to cirrhosis will be assessed in the subset of subjects considered noncirrhotic at Baseline using available medical history, clinical, and laboratory assessments as well as Baseline transient elastography (TE), where available. Specifically, subjects with no clinical, laboratory, or radiological evidence of cirrhosis at baseline and/or a TE liver stiffness of <16.9 kPa (Corpechot 2012) will be considered noncirrhotic. Progression to cirrhosis will be assessed by the development of clinical, laboratory, or radiological evidence of cirrhosis and/or when liver stiffness increases to ≥ 16.9 kPa during the study in which case histological progression to cirrhosis should be confirmed by biopsy unless not medically indicated. Using this definition for progression to cirrhosis, the percentage of noncirrhotic subjects progressing to cirrhosis during the treatment period will be summarized by treatment group and compared using a Cochran–Mantel–Haenszel test stratified by the randomization stratification factor.
 
For those subjects enrolled in the biopsy substudy (defined in Addendum 2) progression to cirrhosis identified by the above criteria and improvement in fibrosis/cirrhosis will be confirmed by paired biopsy. Analyses for the histological assessment conducted as part of the biopsy substudy are defined in Addendum 2.
	
Rationale 11

Synopsis, Statistical
	
Safety data, including AEs, vitals, electrocardiogram, and clinical laboratory results
	
Safety data, including AEs, vitals, electrocardiogram, and clinical laboratory results
	
Clarification of summary analyses.

Section	Original Text (Amendment 3, 07 September 2016)	Revised Text (Version 4, 10 May 2017)	Justification for Change
Methods, Safety Analyses	will compare OCA and placebo using the Safety Population.	will be summarized by treatment group for the Safety Population.	

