
Section 9.7.3.2 Progression to Cirrhosis
	
Insertion
	
9.7.3.2 Progression to Cirrhosis
 
When a subject identified as noncirrhotic at Baseline per the criteria listed in Section 9.7.3.1 exhibits any signs or symptoms associated with progression to cirrhosis, as defined by the same criteria, the subject should also be assessed by Fibroscan® TE where available and progression to cirrhosis
	
Details the assessment of progression to cirrhosis.
				

Section	Original Text (Amendment 3, 07 September 2016)	Revised Text (Version 4, 10 May 2017)	Justification for Change
		
confirmed by biopsy (centrally read) unless not medically indicated. Laboratory samples needed to obtain noninvasive scores of liver fibrosis (ELF, and aspartate aminotransferase to platelet ratio index [APRI]) will also be collected when a subject develops evidence of progression to cirrhosis.
 
Full instructions concerning the sample collection methods, processing, labeling, and shipping will be provided by the Sponsor in a study-specific histology manual. Collection supplies will be provided by the central laboratory.
 
Sites participating in the paired biopsy substudy must confirm progression to cirrhosis by biopsy as per the information outlined in protocol Addendum 2.
 
All suspected cases of progression to cirrhosis should be submitted for adjudication regardless of the availability of transient elastography or biopsy results.
	

Section 9.7.6 Screening Procedures
	
Two Screening visits will occur from 1 to 8 weeks prior to Day 0 (as outlined below) allowing for the collection of repeated serum chemistry samples (at least 2 weeks apart) to confirm pretreatment ALP and total bilirubin values:
 
Insertion
	
Collection of 2 serum chemistry samples (collected at least 2 weeks apart) during Screening is required for confirmation of the pretreatment serum chemistry values, including the ALP and total bilirubin used to determine eligibility:
 
 • When the 2 bilirubin or ALP assessments collected at Screening Visit 1 and Screening Visit 2 differ by $\geq 30\%$, a third sample must be collected at an unscheduled visit as a confirmatory sample to include in the mean result(s) that will be used to determine eligibility. 	
Allows repeat assessments when baseline laboratory values are discrepant between Screening Visit 1 and Screening Visit 2.

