Liver biopsies will generally be obtained from the right lobe of the liver as described in a study-specific histology manual. If the initial biopsy was obtained from the left lobe, then subsequent biopsies should be obtained from the left lobe, and vice versa.

All biopsy assessments, including screening and histology efficacy assessments, will be performed by study pathologist/central reader blinded to the treatment group assignment. The biopsies will be graded by a central reader using a pre-defined scoring system. Detailed information related to biopsy scoring will be provided to the central reader by the Sponsor in a study-specific histology manual.

Paired biopsies (Screening/Baseline biopsy and post-treatment [or EOT/EOS] biopsy) will be read by a central reader blinded to the treatment group assignment.

Biopsy Criteria for Progression to Cirrhosis

The following criteria will be used for adjudication of progression to cirrhosis:

- Persistent (ie, 2 consecutive measurements obtained at least 3 months apart) elevation in Fibroscan® TE >16.9 kPa, AND/OR
- Presence of any of the following:
 - Gastroesophageal varices
 - Ascites
 - Radiological evidence of cirrhosis (nodular liver or enlargement of portal vein and splenomegaly)
 - Combined low platelet count (<140,000/mm³), with any of the following criteria:
 - Persistent decrease in serum albumin, OR
 - Elevation in prothrombin time/international normalized ratio (not due to antithrombotic agent use), OR
 - Elevated total bilirubin >2x upper limit of normal

Transient Elastography

TE assessment will be performed at the investigational sites, where the device is available, using the Fibroscan instrument (Echosens, Paris, France), to assess liver fibrosis.

Noninvasive Scores of Liver Fibrosis

ELF score will be calculated using an algorithm that combines serum values of tissue inhibitor of metalloproteinases-1, procollagen type-3 N-terminal propeptide, and hyaluronic acid. Likewise, APRI score will be obtained from serum aspartate aminotransferase and platelet values.

ASSESSMENT OF SAFETY

Safety assessments will be performed as in Section 12 of the main protocol. In addition, the Investigator will document her/his opinion of the relationship of the adverse events (AEs) to liver biopsy using the criteria outlined in [Table 2](#).

Table 2: Relationship of Adverse Events to Liver Biopsy

Relationship	Description

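### The secondary endpoint of progression to cirrhosis has two conflicting elastography criteria, and where no biopsy is done a single high reading can count under Section 13.1.5 but not under the Addendum 2 adjudication list

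*Protocol*

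**What the plan says.** **Main protocol, Section 13.1.5** (revised text in Appendix I; Appendices J and K list no change to it). In subjects noncirrhotic at baseline, progression is assessed by clinical, laboratory or radiological evidence and/or "when liver stiffness increases to ≥ 16.9 kPa during the study". The sentence continues: "in which case histological progression to cirrhosis should be confirmed by biopsy unless not medically indicated". This definition then supplies the percentages compared by a stratified Cochran-Mantel-Haenszel test. For substudy subjects the same section says that "progression to cirrhosis identified by the above criteria and improvement in fibrosis/cirrhosis will be confirmed by paired biopsy".

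**Main protocol, Section 9.7.3.2** (moved to Section 7.5.4 in Version 5). Work-up starts when a noncirrhotic subject "exhibits any signs or symptoms associated with progression to cirrhosis, as defined by the same" criteria as the list in Section 9.7.3.1. That list includes "Transient Elastography Median Value ≥ 16.9 kPa", and bilirubin at 2 times the upper limit of normal combined with a low platelet count. Confirmatory biopsies are read centrally. All suspected cases go to adjudication, whether or not elastography or biopsy results exist.

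**Addendum 2, Section 6.** "The following criteria will be used for adjudication of progression to cirrhosis", and the first item is "Persistent (ie, 2 consecutive measurements obtained at least 3 months apart) elevation in Fibroscan® TE >16.9 kPa". Its bilirubin item is strictly greater than 2 times the upper limit of normal. The adjudicating body is the hepatic outcomes committee of the main protocol, and the stated aim is that events meet predefined criteria consistently across sites.

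**The concern.** One event, judged by one committee, has two elastography criteria. They differ in the inequality sign and, more importantly, in persistence. Take a subject who reads 17.5 kPa once and 12 kPa six months later and has no biopsy. Section 13.1.5 allows that subject to be counted as progressed; the elastography item in Addendum 2 does not.

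Elastography is scheduled every 6 months, where the device is available, over a minimum follow-up of about 6 years. The subjects are noncirrhotic at baseline partly because they read below the cutoff. A rule met by any single reading collects chance crossings as visits accumulate. If such crossings are equally likely in both arms, they add events that carry no treatment information and shrink the difference between arms.

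**Working it through.** **1. The plan's own figure.** The only figure for this endpoint is the substudy power in Addendum 2: 45 subjects, placebo rate 0.5, one-sided alpha 0.1, close to 1:1 allocation (22.5 per arm).

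- OCA rate 0.23: difference 0.27, pooled rate 0.365. SE under the null = √(0.365 × 0.635 × 2/22.5) = 0.1435. SE under the alternative = √((0.25 + 0.1771)/22.5) = 0.1378. Power = Φ((0.27 − 1.2816 × 0.1435)/0.1378) = 0.734, against 73% stated.
- OCA rate 0.28: the same formula gives 0.594, against 59% stated.

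Both reproduce. They rest on biopsy data, so the conflict below does not alter them.

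**2. The two rules side by side.**

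| | Section 13.1.5 | Addendum 2 |
|---|---|---|
| Elastography threshold | ≥16.9 kPa | >16.9 kPa |
| Repeat reading | none stated | 2 consecutive, at least 3 months apart |
| Bilirubin (with low platelets) | 2 × ULN (Section 9.7.3.1 list) | >2 × ULN |
| Stated use | analysis definition, substudy included | adjudication |
| Biopsy | confirms, unless not medically indicated | report available to adjudicators |

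The conflict also falls inside the substudy: Section 13.1.5 applies its own criteria to those subjects, while Addendum 2 lists the persistent criterion.

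**3. How far the rules can diverge.** The documents give no error rate for elastography. Assume that a truly noncirrhotic subject has an independent chance f of a false high value at each reading, with 6 years × 2 per year = 12 readings and no biopsy or adjudication.

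- Single reading: F = 1 − (1 − f)^12.
- Two consecutive readings: let a = no run yet and last reading low, b = no run yet and last reading high, c = run reached. Start at a = 1 and update 12 times: a′ = (a + b)(1 − f), b′ = a·f, c′ = c + b·f. Then F = c.

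| f | Single reading | Two consecutive |
|---|---|---|
| 1% | 1 − 0.99^12 = 11.4% | 0.1% |
| 2% | 1 − 0.98^12 = 21.5% | 0.4% |
| 5% | 1 − 0.95^12 = 46.0% | 2.6% |

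**4. Effect on the comparison.** If true progression rates are p1 and p2 and false positives strike both arms equally, the observed rates are p + (1 − p)F, and the difference becomes (p1 − p2)(1 − F). The single-reading rule would multiply the true difference by 0.886, 0.785 or 0.540; the two-reading rule by 0.999, 0.996 or 0.974. If only a share u of these cases goes without biopsy, and biopsy corrects the rest, F becomes u × F. At u = one half, the single-reading values of F are 5.7%, 10.8% and 23.0%. Adjudication would lower them further.

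**The case against.** The strongest reply is that the main text already describes a sequence: a high reading prompts a centrally read biopsy, then committee review. A reader might infer that any one-off reading is an event. The documents do not say so, because the sentence containing the threshold goes on to require biopsy where medically indicated, and all suspected cases are adjudicated. This stands. It leaves the cases without a biopsy, for which the two texts give different answers.

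A reader might also infer that the endpoint means one thing in the main study and another in the substudy. That is not established. Addendum 2 does not expressly confine its adjudication list to substudy subjects, so the committee may apply persistence to everyone. The conflict would then lie between the analysis definition and the adjudication criteria, which still need to agree.

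Nor does it follow that substudy subjects cannot be combined with the rest. Section 13.1.5 covers them too, and events could be re-derived from recorded elastography values.

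Three further limits stand. The input is already a median value, errors within a subject may be correlated, and not every site has the device, so the 12-reading model is generous to the concern. A difference in event date does not affect the Cochran-Mantel-Haenszel comparison, although Section 13.1.5 also lists the endpoint among its time-to-event analyses. Current Section 7.5.4, the Version 5 cirrhosis algorithm and the committee charter are not in the part of the protocol at hand and may settle some of this.

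**Conclusion.** The conflict in wording is real and should be resolved before the endpoint is analysed. Its reach is limited to cases that rest on elastography without biopsy, in a secondary endpoint that is neither primary nor key secondary. The biopsy-based substudy analysis and its 73% and 59% powers are untouched.

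The 11% to 46% against 0.1% to 2.6% are illustrations. They are upper bounds for each assumed false-high rate, before biopsy and adjudication, and they rest on independent errors and 12 completed readings. Correlated errors would narrow the gap between the rules. The direction does not depend on the assumed rate: two consecutive readings cannot produce more false events than a single reading from the same series.

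**What to change.** Reconcile Section 13.1.5, Section 9.7.3.2 (now within 7.5.4) and Addendum 2, Section 6, for the efficacy endpoint only:

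- one inequality sign at 16.9 kPa;
- for elastography-only cases without biopsy, the two-reading persistence rule already in Addendum 2, in all adjudicated subjects;
- a single high reading serves only as the trigger for work-up and submission to the committee;
- one bilirubin cutoff for the endpoint;
- a stated event date, for example the first of the two confirming readings.

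The cirrhosis criteria that set the dosing regimen share the Section 9.7.3.1 list and should not be altered by this edit, so the endpoint definition needs its own wording.

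The cost is text in the protocol, the addendum and the adjudication criteria. No visit is added, because six-monthly elastography supplies the second reading. The price is that an elastography-only event is confirmed up to 6 months later, and a high value at a subject's last reading stays unconfirmed.

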
Section 13.1.5 Additional Secondary Efficacy Analyses
	
The following secondary efficacy analyses will compare randomized OCA to randomized placebo on using the ITT population:
	
The following time-to-event secondary efficacy analyses will compare OCA versus placebo using the ITT population:
 
 • Progression to cirrhosis • Time to occurrence of HCC 	
Editorial Change Progression to cirrhosis added as secondary endpoint in Version 3.1. HCC has been redefined as a secondary endpoint instead of a component of the primary composite-event endpoint per Regulatory Authority request.

Section 13.1.5.1 Association of Biochemistry with Clinical Outcomes and Clinical Benefit
	
The association between the effect of OCA on ALP and bilirubin and the clinical benefit of OCA will be evaluated by estimating the proportion of net treatment effect on the primary composite endpoint that is explained by each biochemical marker. For each biochemical endpoint, this proportion will be estimated by applying the partial likelihood function to two Cox models that use the same failure time variable, as described in Lin 1997. This analysis will be based on the ITT population. Based on the association between biochemical changes and clinical outcomes described above, clinical benefit of OCA for key subpopulations of interest will be evaluated. This analysis will be further described in the SAP.
	
The association between biochemistry including ALP and bilirubin with clinical outcomes will be assessed and the clinical benefit of OCA using biochemistry as a surrogate endpoint will be evaluated. Detailed analysis will be described in the SAP. Based on the association between biochemical changes and clinical outcomes described above, clinical benefit of OCA using biochemistry as a surrogate endpoint for key subpopulations of interest will be evaluated. This analysis will be further described in the SAP.
	
This analysis will provide additional insight into the connection between surrogate endpoints and clinical outcome events allowing for evaluation of benefit in subpopulations for which the study is not powered.

Section	Original Text (Amendment 3.1, 21 December 2016)	Revised Text (Version 4, 10 May 2017)	Justification for Change

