
Synopsis, Statistical Methods, Primary Efficacy Endpoint
 
Section 11.1.1 Primary Assessments
	
The primary efficacy endpoint will be the time to first occurrence of one of the following post randomization:
 
 • Encephalopathy (as defined by a West Haven score of ≥ 2) • Hepatocellular carcinoma confirmed by 2 complimentary imaging modalities 
Change in Synopsis section Every event for enrolled subjects will be adjudicated by an independent committee.
	
The primary efficacy endpoint will be the time to first occurrence of one of the following:
 
 • Hepatic encephalopathy (as defined by a West Haven score of ≥ 2) 
All events will be adjudicated by an independent committee.
	
Rationale 5

Synopsis, Statistical Methods, Primary Efficacy Analysis
 
Section 13.1.3 Primary Efficacy Analysis
	
The primary efficacy analysis will compare randomized OCA to randomized placebo with respect to the primary efficacy endpoint using the ITT population.
 
Insertion
	
The primary efficacy analysis will compare OCA to placebo with respect to the primary efficacy endpoint using the ITT population.
 
The same analyses for primary efficacy endpoints will be performed for PP population as a sensitivity analysis.
	
Rationale 12

Synopsis, Statistical Methods, Key Secondary Efficacy Analyses
 
Section 13.1.4 Secondary Efficacy Analysis
	
The key secondary efficacy analyses will compare randomized OCA to randomized placebo in ITT population with respect to the key secondary efficacy endpoints.
 
Insertion
	
The key secondary efficacy analyses will compare OCA to placebo in the ITT population with respect to the key secondary efficacy endpoints.
 
The same analyses for key secondary efficacy endpoints will be performed for PP population as a sensitivity analysis.
	
Rationale 12

Synopsis, Statistical Methods, Additional Efficacy Analyses
	
Other Efficacy Analyses
 
The following secondary efficacy analyses will compare OCA to placebo on time to the following events:
	
Additional Efficacy Analyses
 
The following time-to-event secondary efficacy analyses will compare OCA to placebo using the ITT population:
 
 • Progression to cirrhosis • Time to occurrence of HCC 	
Rationale 6 and Rationale 11

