
Section 5.5.2.1 Rationale for OCA Dose
	
The Phase 3 PBC study subsequently evaluated the safety and efficacy of OCA at lower doses of 5 mg (titrated to 10 mg after 6 months based on efficacy and tolerability in the double-blind phase and after 3 months in the open-label phase) and 10 mg;
 
Insertion
	
The Phase 3 PBC study (Study 747-301) subsequently evaluated the safety and efficacy of OCA at lower doses of 5 mg (titrated to 10 mg after 6 months based on efficacy and tolerability in the double-blind phase and after 3 months in the open-label phase) and 10 mg;
 
Study 747-301 demonstrated that titration of OCA from a starting dose of 5 mg to 10 mg improved tolerance to pruritus relative to 10 mg (56% versus 69% of subjects who experienced pruritus) and minimized dropouts due to pruritus.
 
Based on these data, the approved dosing regimen for OCA for the treatment of patients with PBC are 5 mg and 10 mg.
	
Provides rationale for the dosing in alignment with commercial labeling.

Section	Original Text (Amendment 3, 07 September 2016)	Revised Text (Version 4, 10 May 2017)	Justification for Change
	
Based on these data, the indicated commercial doses of OCA for the treatment of patients with PBC are 5 mg and 10 mg.
 
As such, Study 747-302 will evaluate the effect of OCA on clinical outcomes using the 5 mg OCA dose increasing to 10 mg OCA, if tolerated.
	
Study 747-302 will evaluate the effect of OCA on clinical outcomes using the 5 mg OCA dose for at least 3 months, increasing to 10 mg OCA, if tolerated.
	

Section 5.6 Summary of Known Potential Risks with OCA
	
These findings were seen more frequently with doses above 10 mg OCA.
 
Insertion
	
These findings were seen more frequently with doses of OCA 10 mg once daily to OCA 50 mg once daily (up to 5x the highest recommended dose).
 
Refer to the Investigator’s Brochure (IB) for additional information regarding the known potential risks with the investigational product.
	
Language has been updated to reflect Sponsor standards.

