
Section 13.1.12 Continuous Monitoring and Interim Analyses
	
Insertion
	
13.1.12 Continuous Monitoring and Interim Analyses
 
Blinded safety reports including the accrual of events, drop outs, and/or loss of subjects to commercially available OCA will be reviewed by the DMC on a regular basis.
 
Two planned interim analyses of the liver-related outcomes will be conducted using the Lan-DeMets O’Brien-Fleming boundaries (Reboussin 2000). Both interim analyses will be pre-specified and will occur after accrual of 50% (64 events) and 75% (96 events) of clinical outcome events, respectively.
 
The DMC will review the available efficacy data in conjunction with detailed safety data and other relevant information to recommend continuation, modification, or cessation (for efficacy) of the study beyond each interim analysis. Modification of the study would not take place without prior agreement with regulatory authorities.
	
Two Interim Analyses have been added to the protocol.

Section 19 List of References
	
Insertion
	
Beuers U, Gershwin M, Gish R, et al. Changing nomenclature for PBC: From
	
Additional relevant references were added.

Section	Original Text (Amendment 3, 07 September 2016)	Revised Text (Version 4, 10 May 2017)	Justification for Change
		
‘cirrhosis’ to ‘cholangitis’. Digestive and Liver Disease. 2015a;47(11):924-6.
 
Beuers U, Gershwin M, Gish R, et al. Changing nomenclature for PBC: From ‘cirrhosis’ to ‘cholangitis’. Gastroenterology. 2015b;149(6):1627-9.
 
Beuers U, Gershwin M, Gish R, et al. Changing nomenclature for PBC: From ‘cirrhosis’ to ‘cholangitis’. Hepatology. 2015c;62(5):1620-2.
 
 
 
	

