7.6, Dose Adjustment, Interruption, and Withdrawal from Investigational Product or Study	
Investigational product may be temporarily decreased (eg, from 10 mg twice weekly to 5 mg twice weekly, or from 5 mg twice weekly to 5 mg once weekly) or temporarily or permanently stopped based on tolerability concerns. Investigational product may be resumed at the maintenance dose upon resolution of gastroenteritis or worsening renal function or dehydration if there is no evidence of liver injury. For rechallenge following all other dose interruptions (see Table 7), investigational product should be initiated at a lower dose and subjects monitored more frequently with up-titration considered based on tolerability.
 
Adjustments, interruptions, discontinuation, and any rechallenge of investigational product should be implemented per the criteria outlined in Table 7. Subjects that discontinue investigational product are expected to continue in the study (and follow the regular visit schedule) until the end of the study, and the study will terminate at the time when the needed number of
	
Investigational product may be temporarily decreased (eg, from 10 mg twice weekly to 5 mg twice weekly, or from 5 mg twice weekly to 5 mg once weekly) or temporarily or permanently stopped based on safety and/or tolerability concerns.
 
Investigational product may be resumed at the maintenance dose upon resolution of gastroenteritis or worsening renal function or dehydration if there is no evidence of liver injury. For rechallenge, following all other dose interruptions (see Table 7), investigational product should be initiated at a lower dose and subjects monitored more frequently with up-titration considered based on tolerability.
 
Adjustments, interruptions, discontinuation, and any rechallenge of investigational product should be implemented per the criteria outlined in Table 7. Subjects who discontinue investigational product are expected to continue in the study (and follow the regular visit schedule) until the end of the study, and the study will terminate at the time when the needed number of adjudicated events has accrued. If a subject reaches an outcome event, he or she should continue the regular visit schedule and continue taking investigational product as long as the subject has not met any of the criteria for mandatory interruption of investigational product outlined in Table 7, and the Investigator assesses it as safe to continue. In general, subjects should be strongly encouraged to both stay on investigational product and remain in the study until study termination. If a subject discontinues investigational product and cannot continue to attend regularly scheduled study visits, the subject should be strongly encouraged to participate in study follow-up via phone calls or electronic medical record review as described in Section 7.9.
	Section was revised to reiterate the importance of collecting follow-up information for subjects who discontinue treatment and/or the study

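### Progression to cirrhosis is listed as a time-to-event analysis but tested as a percentage over an undefined treatment period, so unequal stopping could distort it in either direction

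*Protocol*

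**What the plan says.** The text comes from the Version 4 change tables.

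- **Heading of the list.** In Appendix I, the Synopsis and Section 13.1.5 entry introduces progression to cirrhosis with: "The following time-to-event secondary efficacy analyses will compare OCA to placebo using the ITT population". Appendix H has the same for Section 13.1.5: "The following time-to-event secondary efficacy analyses will compare OCA versus placebo using the ITT population".
- **Definition of the event.** The Section 13.1.5 paragraph in Appendix I restricts the analysis to subjects noncirrhotic at baseline. It counts new clinical, laboratory or radiological evidence of cirrhosis, and/or "when liver stiffness increases to ≥ 16.9 kPa during the study".
- **Comparison.** The paragraph then states that "the percentage of noncirrhotic subjects progressing to cirrhosis during the treatment period will be summarized by treatment group and compared". The method it names is the Cochran-Mantel-Haenszel procedure, applied within the strata used at randomization.
- **Follow-up after stopping.** Section 7.6 (Appendix K, Version 6) says: "Subjects who discontinue investigational product are expected to continue in the study (and follow the regular visit schedule) until the end of the study".

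The Version 5 and Version 6 tables (Appendices J and K) contain no entry for Section 13.1.5.

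**The concern.** Two things do not fit together. A Cochran-Mantel-Haenszel test on a percentage is not a time-to-event analysis, so the method contradicts its heading. The window is also stated in two ways: the event is defined over the study but counted over the treatment period.

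On the plain reading of treatment period as time on product, the percentage depends on how long each arm stays on product as well as on how fast it progresses. The documents give reasons why stopping could differ by arm. Pruritus is named as the main OCA-related adverse event (Section 5.7), there are liver-related discontinuation criteria (Section 7.6), and subjects can move to marketed drug (Section 13.1.12: "loss of subjects to commercially available OCA will be reviewed by the DMC on a regular basis"). More stopping on OCA would make OCA look protective. More switching from placebo would remove placebo events from the count and hide a benefit. Meanwhile progression dates after stopping are largely collected, through six-monthly elastography where the device is available (Section 7.1.2) and adjudication of all suspected cases (Section 9.7.3.2 of Version 4), and would go unused.

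**Working it through.** The plan states no power or error rate for this comparison, so there is no figure of its own to reproduce. The check asks how the specified percentage behaves when the drug has no effect.

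**Inputs**
- Follow-up F uniform on 6 to 10 years: Section 13.1.2 assumes 4 years of accrual plus 6 of follow-up.
- 8-year risk of cirrhosis 30% in both arms: assumption, varied from 20% to 50%. The upper end borrows the placebo event rate of 0.5 in the biopsy substudy (Addendum 2), which carries no time frame.
- 150 noncirrhotic subjects per arm: assumption. With 428 randomized 1:1 there are 214 per arm, so this is 150/214 = 70%.
- Stopping hazard s per year: assumption. The part of the protocol shown gives no rate by arm.

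**Formula.** With constant hazards, λ = −ln(0.70)/8 = 0.0446. Put k = λ + s. The expected percentage progressing before stopping is

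P(s) = (λ/k) × [1 − A(k)], with A(k) = (e^(−6k) − e^(−10k)) / (4k).

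- s = 0.03: k = 0.0746, λ/k = 0.598, A = 0.553, so P = 0.598 × 0.447 = 26.7%.
- s = 0.08: k = 0.1246, λ/k = 0.358, A = 0.373, so P = 0.358 × 0.627 = 22.4%.

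**Rejection rate at 8 versus 3% per year.** The difference is 0.043. Its standard error is √(0.267×0.733/150 + 0.224×0.776/150) = 0.0497, so the test statistic is shifted by 0.043/0.0497 = 0.866. The rejection probability is Φ(0.866 − 1.96) + Φ(−0.866 − 1.96) = 0.137 + 0.002 = 13.9%, almost all in favour of OCA.

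| Stopping per year, OCA / placebo | Expected percentages, OCA / placebo | Two-sided rejection, no true effect |
|---|---|---|
| 3% / 3% | 26.7 / 26.7 | 5.0% (simulated 4.8%) |
| 4% / 3% | 25.8 / 26.7 | 5.4% |
| 5% / 3% | 24.9 / 26.7 | 6.6% |
| 6% / 3% | 24.0 / 26.7 | 8.4% (simulated 8.7%) |
| 8% / 3% | 22.4 / 26.7 | 13.9% (simulated 13.7%) |

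Swapping the arms gives the same rates in the opposite direction.

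**Sensitivity.** At 8 versus 3% per year, rejection is about 10.6% if the 8-year risk is 20% and about 22% if it is 50%.

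**Counting all follow-up.** Repeating the 8 versus 3% case with events counted over the whole study gives 4.9%. The distortion therefore comes from the on-treatment window combined with unequal stopping. Staggered entry alone does not produce it.

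**Time-to-event comparison.** In 4000 simulated null trials at an 8-year risk of 50%, a stratified log-rank test with time censored at stopping rejected in 4.8% to 6.0% of trials in every stopping scenario. The percentage test rejected in 20.8% at 10 versus 5% per year (OCA versus placebo). With a true hazard ratio of 0.60, the percentage test had 91.7% power when OCA stopped more (10 versus 5%) and 26.4% when placebo did. The log-rank test had about 68% either way.

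**The case against.** 1. **The current text is not in view.** Only change tables and addenda are shown. That the wording survives in Version 6 is inferred from the absence of a Section 13.1.5 entry, and those tables omit minor edits. This stands and limits confidence. Both conflicting statements are Version 4 revised text, however, so this is not old wording set against new, and replacing a hypothesis test would hardly be a minor edit.
2. **Treatment period is not defined in the part shown.** It could mean the whole double-blind period, and the sentence refers back to a definition that speaks of the study. On that reading the exposure bias disappears. This stands: the bias is conditional. The mismatch between heading and method does not depend on it.
3. **The list heading may simply be loose.** In the fuller Synopsis list in Appendix H, the other entries begin with the words time to, and this one does not. The percentage test may be what was intended. That explains the conflict without resolving it.
4. **The rates are assumed.** At 4 or 5 versus 3% per year the inflation is slight. Section 5.5.2.1 says that titration in the earlier Phase 3 study "minimized dropouts due to pruritus", which weakens the case for heavy stopping on OCA. This stands.
5. **Detection after stopping is incomplete.** Subjects who move to telephone contact or record review (Table 8 in Section 9.7.15) have no scheduled elastography or ultrasound. This stands, and any analysis over the whole study inherits it.

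A reader might infer that the test is known to favour OCA, that the 6 to 10 year spread of follow-up biases it, or that the trial's main result is at risk. The documents support none of these. Stopping by arm is not given and could run either way. Randomization balances staggered entry. The endpoint is neither primary nor key secondary.

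**Conclusion.** The contradiction is real and should be fixed; confidence is moderate because the Version 6 body text is not shown. The plan gives one endpoint a time-to-event heading, a percentage test and two different windows, so two analysts following it could reach different results.

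The statistical harm rests on two conditions: that treatment period means time on product, and that stopping differs between arms. If both hold, type I error under the assumptions above rises from about 5% to between 5 and 7% at 4 to 5 versus 3% per year, about 8.5% at 6 versus 3%, and about 14% at 8 versus 3%. More stopping on OCA falsely favours OCA; more switching from placebo to commercial OCA hides benefit. If either condition fails, what remains is a drafting conflict over method and window.

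**What to change.** In Section 13.1.5 and the Synopsis, make the comparison match its heading. Define the endpoint as time from randomization to first adjudicated progression in all ITT subjects noncirrhotic at baseline, counted over the whole study regardless of investigational product. Test it with a log-rank test and estimate the effect with a Cox model, both stratified by the randomization strata. Treat death and liver transplant as competing events (cause-specific hazard, with cumulative incidence curves). Keep the percentage as description, and replace the treatment-period phrase with the same study-long window.

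The cost is wording and some extra programming; no new data are needed. Two limits remain. Subjects on telephone or record-review follow-up will have less complete detection, which should be stated or examined in a sensitivity analysis. Placebo subjects who switch to commercial OCA will still dilute any effect, but this is inherent in the ITT comparison that the heading promises.
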